This study is a pilot trial investigating the feasibility of using activity monitoring data to adjust insulin pump therapy and prevent hypoglycemia. The study will enroll 20 patients 1-17 years old with type 1 diabetes mellitus on insulin pump therapy. Subjects will be provided with continuous glucose monitors (DexCom G4) and FitBit activity monitors. Study duration will be 3 to 4 months. During the course of the study patients will continue to receive routine care by their primary endocrinologist and DNE. Insulin dose adjustments unrelated to activity monitor data will continue to be at the discretion of the patient's primary diabetes team.

Activity level (steps and calories burned) will be uploaded over the web in a secure fashion to our central firewall-protected database on a daily basis while

CGM glucose values and insulin pump data will be collected once a week. Data from the activity monitor is automatically sent to a secure study team RedCap database once a day. This occurs by automatic, wireless syncing of the activity monitor with the patient/family's computer or smartphone. The activity monitor and activity monitor data is not associated with any personal health information. The activity monitor is only set up with a study identification number. Only study team members have access to the list of study identification numbers and associated patient information and this is stored in a secure computer a locked office. CGM and insulin pump data will be downloaded onto a patient or study team computer and then emailed to the study team once a week. Families will also have the option of coming to clinic once a week and having a study team member download the CGM and insulin pump data for them.

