Insulin Pump Therapy: Participants will continue to use their own insulin pump and home blood glucose meter. All subjects will continue to receive routine care from their primary diabetes team. We propose to enact insulin dosing changes if we discover significant hyperglycemia and informing the diabetes providers of these changes." All other insulin dose changes unrelated to activity monitor data and energy expenditure estimates will be at the discretion of the primary team. We recognize that initial use of CGM may reveal previously undetected hypo- or hyperglycemia. Subjects and their families should discuss these findings with their primary diabetes team as they would for any other concerning blood glucose levels. If significant nocturnal hyperglycemia is detected, an increase in nighttime insulin basal rate will be recommended by the study team after being reviewed by the study endocrinologist. The dosing changes to address the hyperglycemia will be made by the study team directly in order to prevent delays in correction of the hyperglycemia as can occur if forced to wait for a response from the primary provider. Nevertheless, Tte recommended changes will also be sent as a powerchart message to the subject's primary diabetes care team and they will be given the option to opt out of the recommendation and contact the patient directly to address the discovered hyperglycemia. If the provider responds after the changes have been enacted then we will simply contact the family and ask them to resume their prior settings and discuss with their provider an alternative plan to treat the hyperglycemia.

Changes in Pump Therapy Based on Activity: During the first two to six weeks of the study, a baseline activity level will be established for each subject (average and standard deviation of first 14 days of available data). High activity

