Data analysis will begin by calculating the baseline (average and standard deviation) activity level for each subject during the first two to six weeks. High activity days will be defined as any day where the activity is greater than one standard deviation above the mean. Correlations will be performed to assess if there is relationship between daytime activity (8- am to 9 pm) and nighttime nadir blood glucose level (continuous). Nadir glucose will also be categorized as hypo- or no-hypo (binary), with a binary logistic regression model used to assess the significance of daytime activity, insulin dosing, and carbohydrate intake, as independent factors increasing the risk of hypoglycemia. Analysis will proceed with generalized estimating equations (not powered but in preparation of the larger study to be conducted). Characteristics of the nighttime glucose profile (nadir glucose, time in target, time below target) will be calculated weekly, with mean and 95% confidence plotted by week. In the event usual-care pump settings are adjusted during the course of the study, the average nighttime glucose values observed for the week following the most recent adjustment will be compared to average values obtained during the final week (assures improvements are due to the availability of the FitBit data rather than the CGM data). Chi2 analysis will be used to assess differences in the incidence of hypoglycemia. Statistical analyses will be performed both as intention to treat and per protocol. The intention to treat analysis will include all data; per protocol analysis will exclude cases in which the subject does not comply with recommendations of the study team or does not complete all 12 weeks of the study. The algorithm will be considered feasible if all data can be assembled, and recommendations deemed reasonable (accepted) in a majority of cases.

Statistical Power and Sample Considerations

This is a feasibility study and therefore is not powered; however, the choice of 10 subjects with any one group is generally considered acceptable for feasibility/pilot-studies and should provide sufficient data to power a larger study.

Study Organization

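### The activity analyses in section 5.a have no study-time term, so a shared drift in activity and night glucose could create or mask the activity association

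*Combined protocol and SAP*

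**What the plan says.** Section 5.a (Data Analysis Plan) sets out three linked analyses.

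- Continuous nadir: "Correlations will be performed to assess if there is relationship between daytime activity" and the overnight nadir. No covariates are named.
- Hypoglycemic night, yes or no: a "binary logistic regression model used to assess the significance of daytime activity, insulin dosing, and carbohydrate intake, as independent factors".
- Then: "Analysis will proceed with generalized estimating equations". Neither covariates nor a working correlation is given.

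Time enters elsewhere in 5.a, apart from the activity models. Night-profile summaries "will be calculated weekly, with mean and 95% confidence plotted by week". There is also a guarded comparison: "In the event usual-care pump settings are adjusted during the course of the study, the average nighttime glucose values observed for the week following" the latest adjustment are set against the final week, so that any improvement can be credited to the activity data and not to CGM.

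Other sections explain why night glucose may move. Section 4.a states "Study duration will be 3 to 4 months" and leaves usual-care dose changes with the primary team throughout. It makes no activity-based changes in the first 2 weeks and afterwards recommends an alternate basal rate on high-activity days. Section 4.c (Insulin Pump Therapy) says "We recognize that initial use of CGM may reveal previously undetected hypo- or hyperglycemia" and lets the study team recommend a higher night basal rate for nocturnal hyperglycemia. Section 4.d states that the pilot has no planned hypothesis and that its data will be used to power a larger study.

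**The concern.** The specific aim depends on whether a more active day is followed by a lower night. That is a day-to-day relation within a child. An analysis pooled over 12 or more weeks without a time term also picks up slow trends. If activity falls over the study while CGM-led care removes lows, early nights are both more active and lower, and the hoped-for association appears with no day-to-day effect. If activity and night glucose both rise, a real effect is hidden. GEE allows for repeated nights within a child when it computes standard errors. It does not remove confounding by time.

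The plan sees this problem in one place, where it resets the reference week after a usual-care change, but does not carry the protection into the activity analyses.

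**Working it through.** The documents give no drift, alpha, effect size or power figure, so there is no stated figure to reproduce. The check asks how large a shared drift must be before it matters.

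**Inputs from the documents.** 20 children (4.a); 12 weeks, the per-protocol duration in 5.a, so 12 × 7 = 84 nights and 20 × 84 = 1,680 child-nights.

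**Assumptions.** Linear drift of a (activity) and b (glucose) from start to end of study, in within-child SD units; two-sided 5% tests; the share of glucose drift that passes through recorded insulin.

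**1. Spurious correlation, no true effect.** With time uniform on (−0.5, 0.5), its variance is 1/12, so

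r = (ab/12) / √[(1 + a²/12)(1 + b²/12)]

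- a = b = 0.5: 0.02083 / 1.02083 = 0.020
- a = 0.5, b = 1: 0.04167 / √(1.02083 × 1.08333) = 0.040
- a = b = 1: 0.08333 / 1.08333 = 0.077

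If either drift is zero, r = 0. Reversing one drift reverses the sign of r.

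**2. False positives for the activity–nadir analysis.** Set-up A lets drifts vary between children (SD 0.5) and uses child-clustered standard errors with t(19), 1,500 runs. Set-up B gives every child the same drift and tests a child-centred correlation, 150 runs; its range covers none, half or all of the glucose drift passing through insulin.

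| Drift (activity/glucose) | A, no time term | A, with week term | B, no time term |
|---|---|---|---|
| 0.25/0.25 | 5.3% | 5.3% | – |
| 0.5/0.5 | 11.5% | 5.9% | 8–15% |
| 0.5/1 | 29% | 4.7% | 39–42% |
| 1/1 | 77% | 5.4% | 88–95% |

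A hand check of B uses z = arctanh(r) × √(1680 − 20 − 3), where the root is 40.7. At 1/1, z = 0.0771 × 40.7 = 3.14, giving about 88% rejection. At 0.5/0.5, z = 0.0204 × 40.7 = 0.83, giving about 13%.

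**3. Logistic GEE with activity, insulin and carbohydrate** (set-up B, 20% of nights hypoglycemic, no true effect, 1 SD drift in both):

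| Share of glucose drift through insulin | OR per SD activity, no time | Rejection, no time | OR with time | Rejection with time |
|---|---|---|---|---|
| None | 0.88 | 63% | 1.01 | 11% |
| Half | 0.94 | 24% | 1.00 | 7% |
| All | 1.00 | 7% | 1.00 | 9% |

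These drifts run in the same direction. With opposite drifts the OR inverts (1/0.88 = 1.14), which is the hoped-for direction. At 0.5/0.5 the OR without time is 0.97 to 1.00. With 150 runs, a true 5% rate has a simulation error of √(0.05 × 0.95/150) = 1.8 points, so 3–11% with a time term is roughly nominal for 20 clusters.

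**4. Masking.** The true effect is −0.1 SD glucose per SD activity, with both drifts upward and none through insulin. At 1/1 the OR falls from 1.19 (time included) to 1.03 (omitted), and power from 87% to 8%. At 0.5/0.5 the OR is 1.19 against 1.14, and power 79% against 65%.

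**The case against.** **Half the mechanism is assumed.** Bias needs activity and glucose to drift together. The documents support a change in glucose but state no trend in activity. Season and school term follow the calendar, and children recruited at clinic visits probably start on different dates, so such trends may partly cancel across children. This stands. It makes the concern conditional and its size unknown.

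**Insulin dosing is already a covariate.** Settings changes act through insulin, which the pump downloads record. This stands for the logistic model to the extent shown in step 3, provided the variable captures the night basal rate, which 5.a does not define. It gives the correlation no protection.

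**This is a pilot.** It has no planned hypothesis and is not powered, so rejection rates are a yardstick and not an error rate that the plan controls. The 77–95% describes a correlation below 0.1. Feasibility is judged on assembling the data and on acceptance of recommendations, not on this coefficient. This stands as to consequence. It does not excuse a biased estimate used for planning.

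**The GEE covariates are open.** A time term is not ruled out, and the weekly plots would show glucose drift. That is true, but plots do not adjust the activity estimate, and leaving the term unnamed is the gap.

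**Time is not the only problem.** After baseline, basal rates are altered on high-activity days, so treatment follows the exposure. A time main effect does not address that. This stands and extends the remedy.

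**Conclusion.** The gap is real and inexpensive to close. No study-time term is named in either activity analysis, although the plan anticipates changes in night glucose and guards another comparison against them. The bias is small at drifts of about 0.5 SD and material near 1 SD in both. It is absent when only one of the two drifts. In the logistic model it shrinks or vanishes as more of the glucose drift runs through recorded insulin. All drift sizes, the hypoglycemia rate and the insulin share are assumptions.

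A reader might infer that any drift over the study is credited to activity, or that the feasibility result is in doubt. The documents support neither. The first needs an activity trend they do not describe, and ignores the insulin covariate. The second rests on criteria that do not use the activity coefficient. The consequence is a possibly biased activity estimate carried into planning the larger study.

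**What to change.** In section 5.a:

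1. Replace the bare correlation with a linear GEE of nadir glucose on the child's daily activity, centred within child.
2. Add a common study-week term, linear or in a few multi-week blocks, to this model and to the logistic GEE.
3. For settings changes, use at most one simple time-varying variable, such as before or after a usual-care change. Do not fit separate indicators for each child's settings periods. Two changes per child would add 2 × 20 = 40 parameters against 20 clusters. At an assumed 15% nightly rate with independent nights, 0.85¹⁴ = 10% of 14-night periods would contain no low. That remedy was not tested here.
4. Report the activity estimate with and without the time term, and separately for baseline and intervention. Define those periods by each child's recorded dates, because baseline is 2 weeks in 4.a but two to six weeks in 5.a.

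The cost is a few lines of text and one to a few degrees of freedom. No new data are needed, since daily activity and weekly CGM and pump downloads are already collected. The time term will also absorb some of any genuine slow activity effect, which is why both estimates should be shown.

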seek to determine whether the activity data can identify instances when those settings may need to be adjusted in response to activity, as well as help determine the extent of the dosing change required. Our long-term goal is to create a cloud-based software tool that will alert the patient when the settings may need to be lowered in response to high activity. This is a pilot study to gather data regarding feasibility of using activity monitors to adjust insulin pump therapy and obtain preliminary data to power a larger outcome study. We include children from 1 to 17 years, in order to observe energy expenditure in children of different ages.

3. Preliminary studies

Our prior studies controlling blood glucose have been in fully automated glucose control in individuals with T1D (aka the artificial pancreas), and in physician supervised control of critically ill patients (aka tight glycemic control; TGC). The studies were performed by at Boston Children's Hospital (BCH), and combined CGM with different Proportional-Integral-Derivative (PID) control algorithms to guide insulin dose adjustments in the subcutaneous insulin infusion pumps used by individuals with T1D, and in the intravenous insulin infusion pumps used to manage critically ill patients in the ICU (4-10).

In the current study we plan to use a version of the same algorithm to guide changes in the basal insulin rates used in today's open-loop pump therapy. Specifically, we look to identify more appropriate rates for use during nights following high daytime activity level. It is on these nights that many subjects find it necessary to lower their basal rates. To assess the ability of the PID algorithm to identify and adjust these rates, we performed a preliminary computer simulation study of the algorithm (Figure 1). Such simulations are increasingly being used to assess algorithms used to adjust insulin delivery (11; 12) in advance of performing a clinical studies. In our simulation study, the P and I components of the PID algorithm were used to make a sequence of recommendations on the midnight to 3 am basal rate in order to achieve target glucose values in the range 110-130 mg/dL. Adjustments were made following an equation in the form of:

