The initial 2 weeks of a subject's enrollment in the study will be used to establish his or her baseline activity level and no changes to the insulin regimen will be made based on the activity monitor data. During weeks 3-6 to 12-16, activity data will be reviewed daily and an alternate basal insulin rate will be recommended on days considered to be increased activity days. We will use an adaptive algorithm to help guide suggested nighttime insulin basal rate changes. All recommendations will be reviewed and approved by a study physician prior to implementation. The alternate rate will be derived using the subject's usual care pump settings as an initial starting point from which to make incremental changes in the 3 hour interval leading up to the hypoglycemic event. Target will be the overnight nadir obtained with usual care settings. Residual error (CGM-target) will be used to assess the validity of using the 3 hour window prior to the event to effect lower basal. The patient's primary diabetes team will be informed about the recommended nighttime basal insulin dose change and this will be documented in the patient's medical record in powerchart. The primary diabetes team will not give recommendations regarding nighttime insulin rate dose changes based on activity monitor data; however, they will continue to guide all other aspects of the patient's diabetes management.

b. Patient Selection and Inclusion/Exclusion Criteria

Subjects will be recruited from the outpatient endocrinology clinic based on physician recommendation and approval to approach at Boston Children's Hospital (BCH) as well as through public notice. 20 subjects will be recruited in two different age designations.

Inclusion Criteria:

- Age: 1 to 17 years old
- Type 1 diabetes (as clinically diagnosed by outpatient endocrinologist).
- Treated with insulin pump therapy for greater than or equal 3 months

- Families will need to have access to Wi-Fi and a compatible smartphone in order for the data from the activity monitor and other devices to be transmitted to the research team

Exclusion Criteria:

- Current glucocorticoid use or other medication known to affect insulin action at investigator's discretion.
- Hospitalization within the last month

c. **Description of Study Treatments and Procedures**

RECRUITMENT, SCREENING AND CONSENT:

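### The comparison meant to credit improvement to activity data uses average nighttime glucose, which cannot separate fewer lows from more highs; the planned hypoglycemia measures are not tied to the same two weeks

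*Combined protocol and SAP*

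**What the plan says.** The specific aim (section 1) and the endpoint named for the larger study (section 4.d) both concern nighttime hypoglycemia. Section 4.d sets the threshold at 70 mg/dL.

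Section 5.a has one comparison intended to separate the effect of the activity monitor from that of CGM. It is conditional: "In the event usual-care pump settings are adjusted during the course of the study". When the condition is met, "the average nighttime glucose values observed for the week following the most recent adjustment will be compared to average values" from the last week of the study. The stated purpose is that this "assures improvements are due to the availability of the FitBit data rather than the CGM data". No direction of benefit is given for the average.

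The same paragraph plans other summaries: "Characteristics of the nighttime glucose profile (nadir glucose, time in target, time below target) will be calculated weekly". Each is to be shown for every week as a mean with a 95% interval. The sentence after the comparison plans a chi-squared analysis of hypoglycemia incidence, without naming the periods to be compared. No hyperglycemia measure is listed.

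Target is not defined in section 5.a. Elsewhere the word has two uses: the simulation in section 3 aims for "target glucose values in the range 110-130 mg/dL", and section 4.a says of the algorithm that "Target will be the overnight nadir obtained with usual care settings".

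**The concern.** The intervention lowers basal insulin on nights after active days in order to prevent lows. Its plausible cost is overnight highs. A mean adds the two together, so a higher mean in the final week could be fewer lows, more highs, or both. The mean also covers the whole week, although the alternate rate applies only after high-activity days, so any effect is diluted.

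The pilot is meant to supply the data for powering a larger study of nighttime hypoglycemia. As written, the one contrast built to isolate the contribution of activity data would give no hypoglycemia figure and no figure for the cost in highs.

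**Working it through.** The plan states no effect size, SD or power for this comparison, so there is no figure to reproduce. What follows is illustration, with assumptions marked.

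**1. Direction.** Shift in weekly mean = share of nights × rise in mg/dL × (hours affected / hours of night). Only the size of the rise enters, not where it starts. Moving 50 to 110 and moving 180 to 240 are both rises of 60, so for equal hours and nights the shift is the same. This needs no assumption about variability.

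**2. Size, using the protocol's own illustrative values.** Inputs:
- A low of 50 mg/dL, from the section 3 simulation.
- Correction to 110–130 mg/dL, from the same simulation.
- A 3-hour window (section 4.a).
- High-activity days more than one SD above the mean (sections 4.c and 5.a). If activity is normally distributed (assumption), the share is 1 − Φ(1) = 0.15866, or 1.11 nights a week.
- Night length, which is not defined. Daytime activity runs from 8 am to 9 pm, so the complement is 11 h; 8 h is an assumed alternative.

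Results:
- 11 h: 0.15866 × 60 × 3/11 = 2.6 and 0.15866 × 80 × 3/11 = 3.5 mg/dL
- 8 h: 0.15866 × 60 × 3/8 = 3.6 and 0.15866 × 80 × 3/8 = 4.8 mg/dL

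**3. Size, milder lows (all inputs assumed, 9 h night).**
- 20% of nights, 20 mg/dL, 1 h: 0.20 × 20 × 1/9 = 0.44 mg/dL
- 30% of nights, 50 mg/dL, 2 h: 0.30 × 50 × 2/9 = 3.3 mg/dL

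Together with step 2 this gives roughly 0.4 to 5 mg/dL. A half-hour low lifted only from 60 to 70 on high-activity nights shifts the mean by about 0.1.

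**4. Where the shift is not small.** If the 3-hour low occurs and is corrected on all seven nights, the shift is 60 × 3/11 = 16 up to 80 × 3/8 = 30 mg/dL.

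**5. Noise.** With an assumed night-to-night SD of 30, 40 or 50 mg/dL and all 20 children contributing, the SE of a one-week against one-week difference is SD × √(2/(7 × 20)) = 3.6, 4.8 or 6.0 mg/dL. This ignores child-by-week variation. It also counts children who would not enter a conditional comparison, so it is a lower bound.

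Alternatively, take an assumed SD of within-child change of 10, 20 or 40. The difference detectable with 80% power at two-sided 0.05 is (1.96 + 0.84) × SD/√20 = 6.3, 12.5 or 25.1 mg/dL. Power for a 2.6 mg/dL shift is 21%, 9% or 6%.

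**6. The same event on a direct scale.** Removing the 3-hour low of step 2 lowers percent of night below 70 by 0.15866 × 3/11 = 4.33 or 0.15866 × 3/8 = 5.95 percentage points. A rise from 180 to 240 leaves that measure unchanged.

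**7. Do the other planned analyses fill the gap?** The weekly plots follow study week, not each child's last usual-care adjustment, so they mix in changes prompted by CGM. Section 4.c expects CGM to uncover highs and lows that were previously missed. The chi-squared sentence names no periods. If target meant 110–130 mg/dL, time below it would count values of 71–109 that are not hypoglycemia. If it meant a usual-care nadir, a single value, time in target would have no meaning.

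**The case against.** The strongest reply is that hypoglycemia is analysed. The chi-squared test on incidence comes in the very next sentence, and nightly nadir, which needs no definition of target, is summarised weekly. That stands. A reader might infer that the pilot will have no usable figure on lows, or that a real fall would go unseen; the documents do not support this. The gap is that these measures are not applied to the two weeks on which attribution rests.

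It is also fair that hypoglycemia incidence is the endpoint of the larger study. The pilot has no planned hypothesis, and feasibility is judged on assembling the data and on recommendations being accepted in most cases. No success rule uses mean glucose.

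The phrase about average values could be read as averages of the listed characteristics. The text does not say so, and the same edit would settle it. Time above target could be derived by subtraction, but only once a target range is fixed. The two uses of target quoted above belong to a simulation and to the algorithm, not to the analysis; they show only that section 5.a cannot borrow a definition from elsewhere.

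A reader might also infer that the mean would miss lows but flag highs. That holds only if highs are allowed on every night and lows on a fraction of nights. A 10 mg/dL rise in nightly mean on 20–30% of nights shifts the weekly mean by 2–3 mg/dL, also under one SE.

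Lastly, section 4.c says that for significant nocturnal hyperglycemia "an increase in nighttime insulin basal rate will be recommended by the study team", and a reader might infer that such increases cancel the activity-based reductions in the mean. If they count as usual-care adjustments, the first week restarts after them and they cannot fall between the two weeks. The text does not settle this, so cancellation is possible but not established.

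**Conclusion.** The point holds for this one conditional comparison. Average nighttime glucose cannot show that lows fell or what the fall cost in highs, so it cannot give the assurance that section 5.a claims. That conclusion rests on arithmetic alone.

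The insensitivity is conditional. For occasional lows the shift is about 0.4 to 5 mg/dL, small or at best comparable with an SE of at least 3.6–6.0. For long nightly lows it is 16–30 mg/dL and would not be small. Night length, frequency, depth, duration and SD are assumed or taken from the protocol's simulation.

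The change is worth making because the larger study is to be powered from these data. It is not a fault in the pilot's feasibility criterion, and it is not a verdict on the analysis plan as a whole.

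**What to change.** In section 5.a, keep the two weeks and change what is compared. Within each child, compare:
- mean nightly nadir;
- percent of night below 70 mg/dL, the section 4.d threshold;
- incidence of nighttime hypoglycemia as section 4.d defines it. Percent of night below 70 does not capture the event-merging rules or preventive carbohydrate, so it cannot stand in for incidence.

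Beside these, report percent of night above one fixed upper limit set by the investigators. Mean glucose may stay as a descriptive measure. Use the same cut-offs in the weekly summaries in place of the undefined target, state the hours that count as night, and apply the incidence comparison to these two periods.

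The cost is a little more analysis. The CGM, meter and pump downloads are already collected weekly, and no visit or procedure is added.

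### The final-week comparison cannot show that an improvement comes from the FitBit data rather than from CGM use or the passage of time

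*Combined protocol and SAP*

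**What the plan says.** Section 5a (Data Analysis Plan) provides for the case in which a child's usual-care pump settings change during the study. Average nighttime glucose values "observed for the week following the most recent adjustment will be compared to average values obtained during the final week". The stated reason is that this "assures improvements are due to the availability of the FitBit data rather than the CGM data". The same section plans weekly summaries of the night profile with 95% confidence, and says "Analysis will proceed with generalized estimating equations" without naming model terms for study phase or type of day.

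The design facts that bear on this are elsewhere:

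- Section 4a: "Subjects will be provided with continuous glucose monitors (DexCom G4) and FitBit activity monitors". No CGM-only or other concurrent group is described.
- Section 4a: "an alternate basal insulin rate will be recommended on days considered to be increased activity days", so the intervention targets some nights only.
- Section 4a gives two weeks of baseline without activity-based changes, then "During weeks 3-6 to 12-16, activity data will be reviewed daily". Section 4c says "During the first two to six weeks of the study, a baseline activity level will be established for each subject".
- Section 4c: "We recognize that initial use of CGM may reveal previously undetected hypo- or hyperglycemia". It also lets the study team raise nighttime basal rates for significant nocturnal hyperglycemia.
- Section 4d: the pilot has no planned hypothesis, and its data will be used to power the larger study.

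**The concern.** The rule has a sound purpose. If both weeks share the same usual-care settings, earlier setting changes cannot explain the difference. The plan claims more than that, and four things stand in the way.

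1. With no control, time trend and growing experience with CGM between the two weeks stay in the contrast. So do study-team increases for hyperglycemia, unless they count as usual-care adjustments; Section 5a does not say.
2. As worded, the averages take in every night, while the alternate rate applies after increased-activity days.
3. Nothing places the reference week before activity-based recommendations start, or apart from the final week.
4. A child whose usual-care settings never change has no such comparison.

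A trend could therefore be reported as a FitBit effect, or a real effect on active-day nights could be missed. Either error could pass into the planning of the larger study.

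**Working it through.** The plan gives no effect size, SD or expected trend, so there is no figure of its own to reproduce. The sizes below rest on labelled assumptions; the logical gap does not.

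**Dilution.** Section 5a defines a high-activity day as one above the baseline mean + 1 SD; Section 4c takes these from the first 14 days of available data.

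- Normal activity: P(Z > 1) = 0.159, and 1/0.159 = 6.3-fold.
- Threshold estimated from 14 days: P(t with 13 df > 1/√(1 + 1/14)) = 0.176, or 5.7-fold.
- Other shapes: uniform 0.211 (4.7-fold); log-normal with sigma 1, 0.0905 (11-fold).
- An assumed 20 mg/dL effect on those nights moves the all-night mean by 20 × 0.159 = 3.2 mg/dL (20 × 0.0905 = 1.8 to 20 × 0.211 = 4.2).

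**Drift and contamination.** Take an 84-day study with the last usual-care adjustment on day a. The reference week is days a+1 to a+7 (mean day a+4); the final week has mean day 81.

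- Drift shown, per assumed 10 mg/dL of linear drift from day 1 to day 84: 10 × (81 − (a+4))/83 = 10 × (77 − a)/83.
- Effect left: if the activity-based effect builds linearly from zero on day s to full on day 84, the share left is (81 − s)/(84 − s) minus the reference week's share, (a + 4 − s)/(84 − s), or zero if that week ends by day s. If the effect is immediate, the share is 100% or 0%.

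| Adjustment day a | Drift shown (mg/dL) | Effect left, start day 15, gradual | Same, immediate | Effect left, start day 43, gradual |
|---|---|---|---|---|
| 7 | 8.4 | 67/70 = 96% | 100% | 39/42 = 93% |
| 42 | 4.2 | 35/70 = 50% | 0% | 35/42 = 83% |
| 70 | 0.8 | 7/70 = 10% | 0% | 7/42 = 17% |

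The mean drift shown over a = 1 to 77 is 10 × 38/83 = 4.6 mg/dL. The shortfalls from 100% in the day-7 row are not contamination; they arise because the final week is averaged at day 81 and not day 84.

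**Calendar.** Of 83 possible adjustment days, the reference week lies wholly before recommendations for 7 (a+7 ≤ 14, two-week baseline) or 35 (a+7 ≤ 42, six-week baseline). It overlaps the final week, or runs past the end, for 13 (a+7 > 77).

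**A false finding from drift alone.** Suppose all 20 children have reference week 3 and final week 12, zero FitBit effect, and a two-sided paired t-test at 0.05 (the plan names no test for this contrast). Simulated drift of 0.5, 1 or 2 mg/dL per week gives an apparent change of 4.5, 9 or 18 mg/dL. It is significant in 25%, 72% or over 99% of runs if the SD of the paired difference is 15 mg/dL, and in 12%, 34% or 86% if it is 25.

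**Would an alternative do better?** The night-type-by-phase contrast was simulated with assumed values: 20 children, 84 nights, nadir mean 110 mg/dL, night SD 30–50, between-child SD 15, high-activity shift −15 (child SD 0 or 20), a switch after one or two high-activity nadirs below 70, baseline 14 or 42 days, and 1,000 runs per setting.

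- Phase defined by a fixed start, zero effect: within 1 mg/dL and 1 percentage point of zero in every setting, and still near zero with a 10 mg/dL drift (expected, since that drift was equal on all nights).
- Phase defined by the date of the switch, zero effect, responses varying between children: pooled bias of about −5 to −15 mg/dL and +4 to +15 percentage points of hypoglycemia.

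**The case against.** The strongest reply is that CGM confounding is partly handled. Section 4c tells families not to dose on sensor values and to take CGM findings to the primary team, so resulting setting changes count as usual-care adjustments and reset the reference week. That stands, and it narrows the residual CGM route to alarms, supplemental carbohydrate, family behaviour and study-team increases if these are not counted. It does not touch time trend.

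Second, this is an unpowered pilot without a hypothesis. Feasibility does not depend on this contrast, and the larger study's primary endpoint is nighttime hypoglycemia, not average glucose. That limits the harm and is why the point is not graded higher. The claim of attribution is still made, and Section 5a does not say which estimate will feed the planning.

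Third, dilution biases towards no effect, so it cannot create a false FitBit claim. True; its cost is a missed effect. The 11-fold end also needs very skewed activity (CV 131%); log-normal sigma of 0.3 to 0.5 gives 13–15% of days, about 7-fold. Section 4c also allows the threshold to be changed per child, which would alter these shares.

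Fourth, the contamination shares depend on the calendar. With a day-43 start they are as tabulated; in a 16-week study with a day-15 start, adjustments on days 42 and 70 leave 64% and 36%. The sizes move, but the trade-off remains whenever there is any drift.

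Finally, children without an adjustment still enter the weekly summaries and the GEE step. Correct: they lack this contrast only. The weekly summaries may reveal a trend but do not separate its causes.

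**Conclusion.** The concern holds. One uncontrolled before/after contrast in children who all have both devices cannot assure that a change is due to FitBit data. This follows from Sections 4a and 5a and needs no assumed number. An early reference week leaves most of any drift in the contrast; a late one subtracts most of the effect sought. The size of each error rests on the assumed activity distribution, linear drift, effect build-up and study length. The point should be fixed because the pilot's data are meant to power the larger study; it does not threaten the feasibility conclusion.

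**What to change.** **Wording.** Delete the claim of assurance and call the comparison descriptive. If it is kept, state which changes reset the reference week (including study-team increases for hyperglycemia) and what is done when that week overlaps the recommendation phase or the final week.

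**Analysis.** In the GEE step already planned, use all nights and all children, clustered by child. Estimate the difference between nights after high-activity days and nights after ordinary days, in the recommendation phase against the baseline phase, for nadir glucose and for hypoglycemia (yes/no). Report it with a 95% CI as exploratory, non-randomised evidence.

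Define phase by a start of activity-based recommendations set in advance for each child, once the two-week and two-to-six-week baseline statements in Sections 4a and 4c are reconciled. Do not use the date an alternate profile is first set: under Section 4c, nadirs on increased-activity days feed the algorithm that prompts it, which produces the bias shown above.

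**Cost.** SAP text, one continuous outcome, and terms for night type, phase and their interaction; the data are already collected. The limits should be stated:

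- There are few high-activity baseline nights per child: 14 × 0.159 ≈ 2, or 42 × 0.159 ≈ 7 only if 42 days are usable.
- The simulated SE of 4.4–9.8 gives a 95% half-width of about 9–19 mg/dL. These are empirical SEs, not GEE standard errors from 20 clusters.
- Children who switch late or never dilute the estimate: a true 20 mg/dL after switching showed as about 8–15 (14-day baseline) or 5–12 (42-day).
- The contrast removes trends common to both kinds of night, but not trends or behaviour specific to active days, such as snacks or family basal changes.
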